5.3.5.6 Abnormal Vital Sign Values

Not every vital sign abnormality qualifies as an adverse event. A vital sign result must be reported as an adverse event if it is verified by a repeat assessment and meets any of the following criteria:

- Is accompanied by clinical symptoms

- Results in a change in study treatment (e.g., dosage modification, treatment interruption, or treatment discontinuation)
- Results in a medical intervention or a change in concomitant therapy
- Is clinically significant in the investigator's judgment

It is the investigator's responsibility to review all vital sign findings. Medical and scientific judgment should be exercised in deciding whether an isolated vital sign abnormality should be classified as an adverse event.

If a clinically significant vital sign abnormality is a sign of a disease or syndrome (e.g., high blood pressure), only the diagnosis (i.e., hypertension) should be recorded on the Adverse Event eCRF.

Observations of the same clinically significant vital sign abnormality from visit to visit should only be recorded once on the Adverse Event eCRF (see Section 5.3.5.4 for details on recording persistent adverse events).

5.3.5.7 Abnormal Liver Function Tests

The finding of an elevated ALT or AST ($>3 \times \text{ULN}$) in combination with either an elevated total bilirubin ($>2 \times \text{ULN}$) or clinical jaundice in the absence of cholestasis or other causes of hyperbilirubinemia is considered to be an indicator of severe liver injury (as defined by Hy's law). Therefore, investigators must report as an adverse event the occurrence of either of the following:

- Treatment-emergent ALT or AST $>3 \times \text{ULN}$ in combination with total bilirubin $>2 \times \text{ULN}$
- Treatment-emergent ALT or AST $>3 \times \text{ULN}$ in combination with clinical jaundice

The most appropriate diagnosis or (if a diagnosis cannot be established) the abnormal laboratory values should be recorded on the Adverse Event eCRF (see Section 5.3.5.1) and reported to the Sponsor immediately (i.e., no more than 24 hours after learning of the event), either as a serious adverse event or an adverse event of special interest (see Section 5.4.2).

5.3.5.8 Deaths

Deaths that occur during the protocol-specified adverse event reporting period (see Section 5.3.1) that are attributed by the investigator solely to progression of influenza or any related co-morbidities should be recorded only on the Study Completion/Early Discontinuation eCRF. All other on-study deaths, regardless of relationship to study drug, must be recorded on the Adverse Event eCRF and immediately reported to the Sponsor (see Section 5.4.2).

Death should be considered an outcome and not a distinct event. The event or condition that caused or contributed to the fatal outcome should be recorded as the single medical concept on the Adverse Event eCRF. Generally, only one such event should be

reported. The term "**sudden death**" should be used only for the occurrence of an abrupt and unexpected death due to presumed cardiac causes in a patient with or without pre-existing heart disease, within 1 hour after the onset of acute symptoms or, in the case of an unwitnessed death, within 24 hours after the patient was last seen alive and stable. If the cause of death is unknown and cannot be ascertained at the time of reporting, "**unexplained death**" should be recorded on the Adverse Event eCRF. If the cause of death later becomes available (e.g., after autopsy), "unexplained death" should be replaced by the established cause of death.

Deaths that occur after the adverse event reporting period should be reported as described in Section 5.6.

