5.2.1 Adverse Events

According to the ICH guideline for Good Clinical Practice, an adverse event is any untoward medical occurrence in a clinical investigation subject administered a pharmaceutical product, regardless of causal attribution. An adverse event can therefore be any of the following:

- Any unfavorable and unintended sign (including an abnormal laboratory finding), symptom, or disease temporally associated with the use of a medicinal product, whether or not considered related to the medicinal product
- Any new disease or exacerbation of an existing disease (a worsening in the character, frequency, or severity of a known condition), except as described in Section [5.3.5.10](#)
- Recurrence of an intermittent medical condition (e.g., headache) not present at baseline
- Any deterioration in a laboratory value or other clinical test (e.g., ECG, X-ray) that is associated with symptoms or leads to a change in study treatment or concomitant treatment or discontinuation from study drug
- Adverse events that are related to a protocol-mandated intervention, including those that occur prior to assignment of study treatment (e.g., screening invasive procedures such as biopsies)

Adverse events will be monitored throughout the entire study (enrollment through Day 100 or Early Discontinuation).

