5.2.2 Serious Adverse Events (Immediately Reportable to the Sponsor)

A serious adverse event is any adverse event that meets any of the following criteria:

- Is fatal (i.e., the adverse event actually causes or leads to death)
- Is life threatening (i.e., the adverse event, in the view of the investigator, places the patient at immediate risk of death)

This does not include any adverse event that had it occurred in a more severe form or was allowed to continue might have caused death.

- Requires or prolongs inpatient hospitalization (see *Section 5.3.5.11*)
- Results in persistent or significant disability/incapacity (i.e., the adverse event results in substantial disruption of the patient's ability to conduct normal life functions)
- Is a congenital anomaly/birth defect in a neonate/infant born to a mother exposed to study drug
- Is a significant medical event in the investigator's judgment (e.g., may jeopardize the patient or may require medical/surgical intervention to prevent one of the outcomes listed above)

The terms "severe" and "serious" are not synonymous. Severity refers to the intensity of an adverse event (e.g., rated as mild, moderate, or severe, or according to DAIDS Table for Grading the Severity of Adult and Pediatric Adverse Events; see Section 5.3.3 and Appendix 4); the event itself may be of relatively minor medical significance (such as severe headache without any further findings).

Severity and seriousness need to be independently assessed for each adverse event recorded on the eCRF.

Serious adverse events are required to be reported by the investigator to the Sponsor immediately (i.e., no more than 24 hours after learning of the event; see Section 5.4.2 for reporting instructions).

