5.3 METHODS AND TIMING FOR CAPTURING AND ASSESSING SAFETY PARAMETERS

The investigator is responsible for ensuring that all adverse events (see Section 5.2.1 for definition) are recorded on the Adverse Event eCRF and reported to the Sponsor in accordance with instructions provided in this section and in Sections 5.4, 5.5, and 5.6.

For each adverse event recorded on the Adverse Event eCRF, the investigator will make an assessment of seriousness (see Section 5.2.2 for seriousness criteria), severity (see Section 5.3.3), and causality (see Section 5.3.4).

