5.3.5.10 Lack of Efficacy or Worsening of Influenza A Infection

Medical occurrences or symptoms of deterioration that are anticipated as part of influenza A should be recorded as an adverse event if judged by the investigator to have unexpectedly worsened in severity or frequency or changed in nature at any time during the study. When recording an unanticipated worsening of influenza A on the Adverse Event eCRF, it is important to convey the concept that the condition has changed by including applicable descriptors (e.g., "accelerated influenza A").

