5.4 IMMEDIATE REPORTING REQUIREMENTS FROM INVESTIGATOR TO SPONSOR

Certain events require immediate reporting to allow the Sponsor to take appropriate measures to address potential new risks in a clinical trial. The investigator must report such events to the Sponsor immediately; under no circumstances should reporting take place more than 24 hours after the investigator learns of the event. The following is a list of events that the investigator must report to the Sponsor within 24 hours after learning of the event, regardless of relationship to study drug:

- Serious adverse events (see Section [5.4.2](#) for further details)

- Adverse events of special interest (see Section 5.4.2 for further details)
- Pregnancies (see Section 5.4.3 for further details)

The investigator must report new significant follow-up information for these events to the Sponsor immediately (i.e., no more than 24 hours after becoming aware of the information). New significant information includes the following:

- New signs or symptoms or a change in the diagnosis
- Significant new diagnostic test results
- Change in causality based on new information
- Change in the event's outcome, including recovery
- Additional narrative information on the clinical course of the event

Investigators must also comply with local requirements for reporting serious adverse events to the local health authority and Institutional Review Board (IRB)/Ethics Committee (EC).

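### Deaths attributed solely to influenza stay off the Adverse Event eCRF, which contradicts the protocol's own serious adverse event rules when the fatal worsening was unexpected

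*Combined protocol and SAP*

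**What the plan says.** Section 5.3.5.8 splits deaths in the adverse event reporting period into two groups. The first group is deaths "attributed by the investigator solely to progression of influenza or any related co-morbidities should be recorded only on the Study Completion/Early Discontinuation eCRF". For the second: "All other on-study deaths, regardless of relationship to study drug, must be recorded on the Adverse Event eCRF and immediately reported to the Sponsor". The next paragraph of 5.3.5.8 treats death as an outcome and asks for the condition behind it on the Adverse Event eCRF, without repeating the exemption.

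The general rules read differently:

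- **5.3.5.10:** deterioration of a kind expected from the infection "should be recorded as an adverse event if judged by the investigator to have unexpectedly worsened in severity or frequency or changed in nature". Fatal cases are not excepted.
- **5.2.2:** an adverse event that is fatal is serious. There is no influenza exception.
- **5.4:** serious adverse events are among those the investigator "must report to the Sponsor within 24 hours after learning of the event, regardless of relationship to study drug".

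In the analysis, 6.4 names deaths among the adverse event parameters and lists serious adverse events, including deaths, by treatment received. Section 6.5.1 counts influenza-related deaths, which under 6.5 means PCR-confirmed patients by randomized arm. Sections 2.2 and 3.4.2 speak of the incidence of death without qualification.

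**The concern.** The primary objective is safety against placebo. Section 1.3 names antibody-dependent enhancement as a potential risk of this type of treatment. If it occurred, it could look like progression of influenza, which is the category of death that 5.3.5.8 takes off the adverse event route.

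That route carries three things the completion form is not said to carry: a documented causality answer (5.3, 5.3.4), the EDC-generated report to the Sponsor's safety group (5.4.2.2), and the Sponsor's own medical assessment with the option to upgrade causality (5.5.2, 5.7). Section 3.1.4 depends on causality. One serious event deemed related suspends dosing, as do similar causally related worsenings in two or more patients. A death that never receives a documented causality answer has no clear way into either criterion.

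**Working it through.** The point is textual, so the main check follows one case through the sections.

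**Case A: the patient dies, the investigator attributes death solely to influenza, and judges the worsening unexpected.**

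1. Under 5.3.5.10 the worsening is an adverse event and belongs on the Adverse Event eCRF.
2. Under 5.2.2 it is serious, because it was fatal.
3. Under 5.4 it is due to the Sponsor within 24 hours, whatever the relationship to study drug.
4. Under the first sentence of 5.3.5.8 the death goes only on the completion form. The second sentence reserves the Adverse Event eCRF and immediate reporting for the other deaths.
5. Steps 1 to 3 and step 4 cannot both be followed as written. Neither 5.3.5.8 nor 5.3.5.10 refers to the other, and 5.3.5.8 does not limit progression to the expected course.

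**Case B: the same death, with the course judged anticipated.** The adverse event definition in 5.2.1 covers "exacerbation of an existing disease (a worsening in the character, frequency, or severity of a known condition), except as described in Section" 5.3.5.10. It can be read to mean that an anticipated course is not an adverse event. Then 5.2.2 and 5.4 are not triggered, and there is no direct contradiction.

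**What is lost in Case A if the site obeys 5.3.5.8.** Section 5.3 ties the assessments to the form: "For each adverse event recorded on the Adverse Event eCRF, the investigator will make an assessment of seriousness", together with severity and causality. The EDC report in 5.4.2.2 also starts from the Adverse Event eCRF. With no entry, the protocol specifies no route to either. Section 6.4 does not say whether deaths held on another form are counted. The exclusion of influenza complications in 5.7 concerns the Sponsor's onward expedited reporting and does not release the investigator from reporting to the Sponsor.

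**How likely is any influenza death?** The documents give no rate, and 3.3.3 describes a population chosen for low complication risk. I assume p = 0.01% and p = 0.1%. Section 4.1 gives 47 patients per arm, so n = 3 × 47 = 141 in all and 2 × 47 = 94 on active drug. The chance of at least one death is 1 − (1 − p)^n.

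| Assumed p | n = 141 | n = 94 |
|---|---|---|
| 0.0001 | 1 − 0.9999^141 = 0.0140 (1.4%) | 1 − 0.9999^94 = 0.0094 (0.9%) |
| 0.001 | 1 − 0.999^141 = 0.1316 (13.2%) | 1 − 0.999^94 = 0.0898 (9.0%) |

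These are chances that an influenza death occurs. They are not chances that one is missed, and they are not limited to unexpected worsening.

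**The case against.** The sections can be read together. Because 5.3.5.8 treats death as an outcome, its first sentence might govern only where the death is noted, while the unexpected worsening still goes on the Adverse Event eCRF and is reported. Alternatively, a course that changed in nature is not progression and so falls among the other deaths. Both readings are possible, but neither is written down. The word only, and the contrast with all other deaths, point the other way.

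Several safeguards also reduce the risk:

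- Severe or serious secondary events are recorded separately (5.3.5.3), and an adverse event that leads to hospital admission is serious (5.3.5.11).
- Where a serious event was already reported, its fatal outcome is follow-up: "The investigator must report new significant follow-up information for these events to the Sponsor immediately".
- Sections 3.1.2 and 3.1.4 require immediate contact with the Sponsor about possible stopping events, without depending on the eCRF.
- The Medical Monitor and a safety scientist review blinded data (5.1). The IMC and SOC review unblinded data and influenza complications (3.1.3, 5.7).
- Section 6.2 summarizes reasons for early termination, and 6.5.1 counts influenza-related deaths.

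These stand as partial cover. The stopping-rule contact turns on a judgement of relatedness or a second similar case, and the admission rule needs an admission first. None of them guarantees an adverse event entry, a causality answer or an EDC report for a death with no earlier serious event.

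It is also fair that an investigator who blames influenza alone would often answer no to causality, since Table 4 accepts underlying disease as another etiology. The investigator's own count of related events may therefore not change. What the adverse event route adds is the documented answer, given against a default of related, and the Sponsor's chance to disagree. Finally, 1.3 reports no sign of enhancement in the Phase 2a challenge study. That lowers the concern, but the risk remains named.

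**Conclusion.** The concern holds. For a fatal worsening of influenza judged unexpected, 5.3.5.8 contradicts 5.3.5.10, 5.2.2 and 5.4, and the death can lack a documented causality assessment and an EDC safety report. For an anticipated course there is no direct contradiction. The gap applies mainly where no earlier serious event, such as pneumonia or a hospital admission, was reported.

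The documents show no lost death and no specific delay, and none is claimed. The probabilities rest on assumed death rates. The weight comes from the threshold in 3.1.4, where one related serious event is enough, so a single death outside the route can matter. It should be fixed. The mismatch between influenza-related deaths in 6.5.1 and unqualified death in 2.2 and 3.4.2 is a separate, smaller point and does not drive this conclusion.

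**What to change.** 1. **5.3.5.8.** Reconcile it with 5.2.2, 5.3.5.10 and 5.4. The simplest way is to remove the exemption, so that every on-study death goes on the Adverse Event eCRF and reaches the Sponsor within 24 hours. This goes further than the contradiction strictly requires. The minimum is one sentence stating that the exemption does not cover unexpected worsening of influenza as described in 5.3.5.10.
2. **6.4.** State that all deaths in the as-treated safety population are tabulated by arm, whatever the attributed cause or source form.
3. **6.5.1 (separate point).** Report all-cause death, with influenza-related death as a subset, to match 2.2 and 3.4.2.

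The cost is one paragraph in 5.3.5.8 (one sentence for the minimum version), one line each in 6.4 and 6.5.1, and at most a few extra serious adverse event reports. The stopping criteria in 3.1.4 are not changed.

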5.3.5.9 Pre-Existing Medical Conditions

A pre-existing medical condition is one that is present at the screening visit for this study. Such conditions should be recorded on the General Medical History and Baseline Conditions eCRF.

A pre-existing medical condition should be recorded as an adverse event only if the frequency, severity, or character of the condition worsens during the study beyond that anticipated for the natural course of the condition. When recording such events on the Adverse Event eCRF, it is important to convey the concept that the pre-existing condition has changed by including applicable descriptors (e.g., "more frequent headaches").

5.3.5.10 Lack of Efficacy or Worsening of Influenza A Infection

Medical occurrences or symptoms of deterioration that are anticipated as part of influenza A should be recorded as an adverse event if judged by the investigator to have unexpectedly worsened in severity or frequency or changed in nature at any time during the study. When recording an unanticipated worsening of influenza A on the Adverse Event eCRF, it is important to convey the concept that the condition has changed by including applicable descriptors (e.g., "accelerated influenza A").

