3.1.3 Internal Monitoring Committee and Scientific Oversight Committee

To provide additional assurance of *patient* safety, safety evaluations will also be *conducted* by an IMC and SOC, as defined in a separate IMC/SOC agreement. In contrast to the SMC, which will *continuously* evaluate *blinded adverse events*, the IMC and SOC will periodically evaluate all available unblinded data to assess whether the study data in its entirety suggest a significant toxicity or worsening disease associated with MHAA4549A. As a result, *the IMC/SOC* may recommend stopping further enrollment in the study or other protocol modifications.

The IMC consists of Sponsor representatives from the following functions: Clinical Science, Drug Safety, Biostatistics, and Statistical Programming and Analysis, *and may invite representatives from other functional areas on an ad-hoc basis when additional expertise is required (e.g., Clinical Pharmacology, Research, etc.)*. The IMC members will be unblinded to all patient treatment and assignment. The Clinical Science representative on the IMC will serve as the IMC Chair and will be a person other than the study Medical Monitor. The IMC Chair *and the drug safety scientist on the IMC* will not be involved in the conduct of the study or have any contact with the study investigators or site staff. *Although* the biostatistician and statistical programmer members *of the IMC will be* involved in the conduct of the study, they *will* not have any contact with study investigators, and all discussion within the IMC *will be* kept confidential. All other Sponsor and Contract Research Organization personnel involved in the conduct of the study will remain blinded to individual treatment assignments.

The SOC members will consist of *at least* two external experts in the field, *and* additional experts may be added to the SOC by the IMC during the course of the study. *SOC members will also be unblinded to study treatment assignments.*

A detailed description of the procedures, data flow, and meeting schedule of the IMC and SOC are provided in a separate IMC/SOC agreement.

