3.4.2 Secondary Outcome Measures

- Time to alleviation of all symptoms (nasal congestion, sore throat, cough, aches, fatigue, headaches, chills/sweats) with resolution maintained for 24 hours (without use of symptom relief medications) as defined by a rating 0 (none) or 1 (mild) for each symptom on a 4-point scale of 0–3. For patients who enroll with mild symptoms, the symptom score must be reduced by 1 point during the study duration.
- Incidence of reinfection or relapse with influenza at 100 days after end of treatment
- Incidence of hospitalization for influenza-related complications at 100 days after end of treatment and length of stay
- Antibiotic usage for secondary bacterial respiratory infections
- Incidence of complications of influenza (e.g., pneumonia, exacerbations of chronic lung disease, myocarditis, acute respiratory distress syndrome (ARDS), otitis media, or other influenza related complications)
- *Incidence of death*

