- Asymptomatic elevations of ALT, AST, and/or amylase without corresponding elevations of bilirubin have been shown to be increased during influenza A infection (Polakos et al. 2006; Yingying 2011).
- Influenza associated disease and/or complications of influenza

An IMC and SOC will monitor the incidence of the above-listed anticipated events during the study. An aggregate report of any clinically relevant imbalances that do not favor the test product will be submitted to health authorities.

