6.4 PRIMARY SAFETY ANALYSES

The safety analyses will include all randomized patients who received study drug, with patients grouped according to the treatment actually received. Safety parameters to be evaluated include adverse events (including deaths, serious adverse events, discontinuations due to adverse events, and the incidence and severity of adverse events), clinical laboratory tests, vital signs, and ECGs. All collected adverse event data will be listed by study site and patient number. All adverse events that occur on or after treatment on Day 1 will be summarized for each treatment group by mapped term, appropriate thesaurus levels, body system, and event within each body system, and toxicity grade. In addition, all serious adverse events, including deaths, will be listed separately and summarized. Serious adverse events caused by a protocol-mandated intervention (e.g., invasive procedures such as biopsies, discontinuation of medications) that occur between consent and first dose of study medication will be listed separately.

Laboratory data with values outside of the normal ranges will be identified. In addition, select laboratory data will be summarized by treatment group using descriptive summary statistics.

The absolute and percentage changes from baseline in vital sign parameters will be computed, and changes deemed clinically significant by the Investigator will be noted. Appropriate descriptive summary statistics will be provided for all vital sign parameters.

The prevalence (baseline) of ATA will be reported and correlation with PK, safety, efficacy, and *biomarker* endpoints will be analyzed as data allow.

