6.5.1 Secondary Endpoints

- Median time to alleviation of clinical signs and symptoms of influenza A infection
- Proportion of patients requiring hospitalization
- Median duration of hospitalization
- Proportion of patients with influenza-related deaths
- Proportion of patients requiring antibiotics for respiratory infection
- Proportion of patients with influenza secondary complications
- Proportion of patients with influenza re-infection

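### Sections 5.2.1 and 5.3.5.10 can be read to leave expected-looking influenza complications off the adverse event record, so the safety tables and SAE counts may understate an excess visible only in aggregate

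*Combined protocol and SAP*

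**What the plan says.** **Recording rule.** Under Section 5.3.5.10, occurrences or symptoms that belong to the expected course of the infection "should be recorded as an adverse event if judged by the investigator to have unexpectedly worsened in severity or frequency or changed in nature". Section 5.2.1 counts any new disease or exacerbation as an adverse event, and then qualifies that limb by pointing to 5.3.5.10: "a worsening in the character, frequency, or severity of a known condition), except as described in Section".

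**Consequences of adverse event status.** Section 6.4 builds the primary safety summaries on what is recorded: "All adverse events that occur on or after treatment on Day 1 will be summarized for each treatment group". Section 5.3.5.11 makes an admission an SAE when it results from an adverse event.

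**What is expected elsewhere.** Section 5.7 lists "Influenza associated disease and/or complications of influenza" among adverse events anticipated in this population. It excludes them from expedited reporting and adds: "An IMC and SOC will monitor the incidence of the above-listed anticipated events during the study". Imbalances unfavourable to the test product go to health authorities. Section 3.4.2 has as a secondary outcome "Incidence of complications of influenza (e.g., pneumonia, exacerbations of chronic lung disease, myocarditis" and others, and Section 6.5.1 analyses "Proportion of patients with influenza secondary complications". Neither section has a condition about expectedness, and neither names a form.

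**The concern.** The primary objective is safety, and Section 1.3 discusses antibody-dependent enhancement as a potential risk of antiviral antibodies. Enhancement could show as a few strange cases. It could also show as more ordinary complications on drug than on placebo, each unremarkable by itself and visible only when the arms are compared. A case-by-case judgement of whether an event was unexpected, made at a blinded site, is poorly suited to the second pattern. If sites apply it to complications, the events drop out of the Section 6.4 tables and the related admissions drop out of the SAE count. If some sites apply it and others do not, the recorded incidence partly reflects site habit. Events not entered at the time may be hard to recover later.

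**Working it through.** **Step 1. Follow one case through the text.** A patient enrolled with uncomplicated influenza develops pneumonia and is admitted. The blinded investigator thinks this a usual course for influenza.

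| Section | Reading A: anticipated, not unexpected | Reading B: new disease or changed nature |
|---|---|---|
| 5.2.1, new-disease limb | falls under the exception | adverse event |
| 5.3.5.10 | no instruction to record | record |
| 5.3.5.11 | no adverse event, so no SAE | SAE |
| 6.4 tables | absent | present |
| 5.7 | complication is on the list to be monitored | same |
| 3.4.2, 6.5.1 | counts, source not stated | counts, source not stated |

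Both readings are open. Reading A conflicts with 5.7, which calls such events adverse events. Reading B leaves the 5.2.1 exception with little to do except cover ordinary symptoms, and the text does not say that this is its scope.

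**Step 2. Look for another capture route.** The Schedule of Activities (Appendix 1) has no row for complications. The diary (Appendix 6) scores seven symptoms and no complication, and Section 5.3.5.13 bars diary data from safety analyses. The Concomitant Medications eCRF would show antibiotics, but it is not said to define a complication. Section 5.3.5.8 also sends deaths attributed solely to influenza progression or related co-morbidities only to the Study Completion/Early Discontinuation form.

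**Step 3. Reproduce the plan's own figures (Section 6.1, Table 5).** Inputs: n = 40 per arm, binomial, true rate p. P(at least 1) = 1 − (1 − p)^40. P(at least 2) = 1 − (1 − p)^40 − 40p(1 − p)^39.

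| p | Computed | Table 5 |
|---|---|---|
| 1% | 33.1% / 6.1% | 33% / 6% |
| 5% | 87.1% / 60.1% | 87% / 60% |
| 10% | 98.5% / 92.0% | 99% / 92% |
| 15% | 99.85% / 98.8% | 99% / 98% |

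The table reproduces; its last row is stated slightly low. Enrolment also agrees: 120 / 0.85 = 141.2, against 141.

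**Step 4. Add incomplete recording.** Table 5 presumes that every event is recorded. Let c be the share of true complications recorded, so the recorded rate is p × c. The documents give no value for c, so it is an assumption. At p = 5% and c = 0.5 the recorded rate is 2.5%: P(at least 1) = 1 − 0.975^40 = 63.7%, and P(at least 2) = 26.4%. The 5% row falls from 87%/60% to 64%/26%.

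**Step 5. Visibility of an imbalance.** Assumptions: 47 dosed per arm (Section 6.1), true rates 5% placebo and 15% active, and the same c in both arms because sites are blinded. Expected counts are 47 × 0.05 × c and 47 × 0.15 × c. P(active count > placebo count) is the sum of the joint probabilities of two independent binomials over all pairs with the active count higher; ties are the pairs with equal counts.

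| c | Expected, placebo vs active | Active higher | Tie | Placebo higher |
|---|---|---|---|---|
| 1 | 2.35 vs 7.05 | 93% | 4% | 3% |
| 0.5 | 1.18 vs 3.53 | 81% | 11% | 8% |
| 0.2 | 0.47 vs 1.41 | 61% | 27% | 12% |

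With 10% vs 20%, the chance that the active arm is higher is 89%, 77% and 60%. The expected ratio between arms does not change with c; the absolute excess shrinks.

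**The case against.** The other side has several good points.

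- **The text does not say only if, and does not name complications.** The adjacent Section 5.3.5.9 does use the stricter form, so the drafters had it available. This stands. The 5.2.1 exception still gives the rule a restrictive effect, which is why the defect is an ambiguity and not a stated exclusion.
- **A new pneumonia may be captured anyway.** Patients with signs of otitis, bronchitis, sinusitis or pneumonia are excluded at entry (4.1.2), so such an event can be called a change in nature. Another limb of 5.2.1, on any unfavourable sign or disease, carries no exception. This is a fair reading, but not the only one.
- **Section 5.7 removes complications from expedited reporting, not from recording.** Correct, and it supports Reading B. It also shows that 5.7 and 5.3.5.10 need reconciling.

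A reader might go further and infer that the complication endpoint, the IMC/SOC check and the safety tables all lose the cases that would reveal enhanced disease. The documents do not support that. The endpoint is not tied to the Adverse Event eCRF. Under Section 3.1.3 the two oversight committees "will periodically evaluate all available unblinded data to assess whether the study data in its entirety suggest a significant toxicity or worsening disease", and their separate agreement is not among the documents. Clearly unexpected worsening is recordable under 5.3.5.10 and appears among the stopping criteria in 3.1.4. The indicators of enhancement cited from the challenge study were viral titers or genomes and symptom scores, which do not pass through this rule.

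The figures are also hypothetical. The event rates and recorded shares have no source in the plan, the comparison of counts is not a planned analysis, and ties account for 27% of outcomes in the lowest 5% vs 15% row. If enhanced cases were more often judged unexpected, the loss would be smaller.

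**Conclusion.** The point holds as an inconsistency in recording rules. As written, a site may keep expected-looking complications out of the adverse event record, and so keep the related admissions out of the SAE count, while other sections presume that these events are counted. The primary safety tables and SAE counts may then understate an excess that only an aggregate comparison would show. Blinded filtering should act about equally in each arm, so it would shrink a true imbalance and not create a false one. Loss from the 6.5.1 endpoint and the 5.7 review is possible but unproven, because their data source is not stated.

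The fall from 93% to 81% or 61% rests wholly on assumed complication rates and recorded shares; if every complication is recorded, nothing is lost. Severity is moderate: worth correcting before data are collected, but not a flaw that by itself prevents the trial from meeting its objective.

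**What to change.** Reconcile Sections 5.2.1, 5.3.5.10, 5.3.5.11 and 5.7:

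1. Limit the filter on unexpected worsening to the ordinary influenza symptoms scored in the diary, and word the 5.2.1 exception to match.
2. State that complications of the kinds listed in 3.4.2, and admissions for them, are always entered on the Adverse Event eCRF, expected or not, with an influenza-complication flag.
3. Name that flag as the source for the 6.5.1 complication endpoint and for the IMC/SOC count in 5.7.
4. In 6.4, tabulate adverse events by arm with and without flagged events.

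The cost is protocol wording, one eCRF field and one extra table. A few more adverse event and SAE entries will follow, with slightly higher adverse event rates in all arms; the paired tabulation keeps that interpretable.
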